7.7 Abnormal Hepatic Function

It is considered as drug-induced liver injury if abnormal AST and/or ALT levels are accompanied with abnormal elevation of TBIL, and the following conditions are met without other possible causes. Such cases shall always be considered as important medical events and be expeditiously reported as per the procedures and time limits.

Table 7. Liver injuries required to be reported as SAEs

Baseline	Normal (AST/ALT and TBIL)	Abnormal (AST/ALT and TBIL)
Treatment	ALT or AST $\geq 3 \times$ ULN with TBIL $\geq 2 \times$ ULN and ALP $\leq 2 \times$ ULN and no hemolysis	ALT or AST $\geq 8 \times$ ULN and TBIL increase $\geq 1 \times$ ULN or value $\geq 3 \times$ ULN

Once being notified with the abnormalities, the subject must return to the study site promptly (ideally within 48 hours) and receive an assessment. The assessment must include the laboratory tests, detailed medical history, and physical assessment, and the possibility of hepatic tumor (primary or secondary) shall be considered.

Other than repeated AST and ALT tests, albumin, creatine kinase, TBIL, direct and indirect bilirubin, γ -GT, PT/INR, and ALP shall also be tested. Detailed medical history include history of alcohol, acetaminophen, soft drugs, various supplements, traditional Chinese medicine, chemical drug exposure, family diseases, occupational exposure, sexual behavior, travel, contact with patients with jaundice, surgery, blood transfusion, hepatic diseases or allergies, cardiac diseases, and immune diseases. Further tests may include the detection of acute hepatitis A, B, C and E, hepatic imaging (such as biliary tract), autoantibodies, and echocardiography. If a retest showed consistency with the criteria outlined in Table 10 and there are no other possible causes, the possibility of drug-induced liver injury could be considered before all the results of etiological tests are accessible. These potentially drug-induced liver injury shall be reported as SAEs, and the Appendix 5: Abnormal Hepatic Function Monitoring and Follow-Up Report shall be submitted to the sponsor.

7.8 Managing of Drug-Related Toxicities

During the course of the trial, the sponsor will conduct regularly monitoring of safety. Detailed information regarding the frequency of review and type of data to be reviewed will be presented in a separate safety review plan.

7.8.1 irAEs

Since the mechanism of action of IBI308 involves T-cell activation and proliferation, irAEs are likely to be observed during this study. Refer to Section 5.4 for the definition of an irAE. Signs and symptoms of irAEs shall be monitored.

Refer to Sections 5.3 and 5.4 for administration adjustments and management of AEs of IBI308. Refer to Appendix 7 (Tables 1 and 2) for a detailed guide on irAE management.

7.8.2 AESIs

AESIs refer to events that require close monitoring in order to enhance the understanding of the safety of the investigational drug. AESIs can be non-serious events.

AESIs for this trial include the followings:

- Infusion reactions \geq grade 3
- Diarrhea/colitis, uveitis, interstitial pneumonia \geq grade 2
- Suspected immune-related AEs \geq grade 3

8 Statistics

8.1 Statistical Analysis Plan

A detailed statistical analysis plan (SAP) will begin to be written after the first enrollment and will be finalized prior to database locking. The SAP will contain details of all analyses and the presentation of results.

8.2 Hypothesis Test

The primary efficacy endpoint is ORR evaluated using the 2014 Lugano Criteria. The hypotheses for the superiority test are as follows:

$$H_0: \text{ORR} \leq 30\%$$

$$H_1: \text{ORR} > 30\%$$

The superiority is determined using confidence intervals (CIs). Superiority of IBI3088 monotherapy for the treatment of relapsed or refractory ENKTL-NT is established if the lower limit of the $(1-\alpha)\%$ CI for ORR is greater than 30% (α may be adjusted according to interim analysis).

8.3 Analysis Population

Analysis population include the safety set (SS), full analysis set (FAS), and per-protocol set (PPS):

- 1) SS: subjects who received at least one dose of the investigational drug.
- 2) FAS: subjects with measurable lesion at baseline and received at least one dose of the investigational drug. Subjects who do not meet the criteria for ENKTL-NT by central pathological review are excluded in the FAS.
- 3) PPS: a subset of the FAS, includes subjects with good compliance and no serious protocol violations or prohibited medications.

8.4 Statistical Methods

8.4.1 General statistical analysis

Variable data will be summarized using the mean, standard deviation, median, maximum, and minimum. Attributes data will be described using frequency and percentage.

All the statistical analyses will be performed with SAS 9.2 (or higher).

8.4.2 Analysis of primary efficacy endpoint

ORR is evaluated using the 2014 Lugano Criteria:

$$ORR = \frac{\text{Number of Subjects with CR + PR}}{\text{Total Number of Subjects}} * 100 \%$$

, superiority is tested using $(1-\alpha)\%$ CI

based on the binomial distribution.

8.4.3 Analysis of secondary efficacy endpoints

- TTR

TTR (CR or PR): time from the first dose to the first tumor response.

The median TTR and corresponding 95% CI will be estimated via the Kaplan-Meier method, and survival curves will be plotted.

- DoR

DoR (CR or PR): time from first date of response to PD or death. Subjects who neither progress nor die will be censored at the date of their last tumor imaging evaluation.

The median DoR and corresponding 95% CI will be estimated via the Kaplan-Meier method, and survival curves will be plotted.

- PFS

PFS: time from first dose to first PD (by imaging), or to death due to any causes. Subjects who neither progress nor die will be censored at the date of their last tumor imaging evaluation. Subjects who did not have any tumor imaging evaluation after baseline will be censored on the date of enrollment.

The median PFS (mPFS) and corresponding 95% CI will be estimated via the Kaplan-Meier method, and survival plots will be plotted.

- OS (investigator-evaluated)

OS: time from first dose to death.

The median OS and corresponding 95% CI will be estimated via the Kaplan-Meier method, and survival curves will be plotted.

- DCR

$$DCR = \frac{\text{Number of Subjects with CR + PR + SD}}{\text{Total Number of Subjects}} * 100 \%$$

, superiority is tested using 95% CI based on the binomial distribution.

8.4.4 Biomarker evaluations

Descriptive summary statistics of PD-L1 expression levels and distribution will be presented, and the association with efficacy will be explored.

The potential association between number of TIL and treatment efficacy will be summarized using descriptive statistics.

Dynamic changes in EBV DNA copy number in peripheral blood will be summarized using descriptive statistics, and the potential association with efficacy will be explored.

Dynamic changes in immune cell phenotypes in peripheral blood will be summarized using descriptive statistics, and the potential association with efficacy will be explored.

The correlation between immune-related cytokines IL-6, IL-15, TNF- α and soluble PD-L1 and efficacy of anti-PD-1 treatment will be presented using descriptive statistics.

Post-hoc analyses may possibly be carried out. The analyses described in this section will be carried out based on the data collected.

8.4.5 Quality of life analysis

The EQ-5D-5L and EROTC QLQ-C30 scores at each evaluation time point will be calculated. The overall score and each dimension score at each time point, as well as relative changes from baseline, will be summarized using descriptive statistics.

8.4.6 Safety analysis

The safety analysis will use the SS. Safety parameters include AEs, laboratory examinations, vital signs, ECG, immunogenicity, etc.

8.4.6.1 Drug exposure

The amount of drug exposure and duration of treatment (number of treatment cycles) will be summarized.

8.4.6.2 AEs

All the AEs will be coded according to MedDRA.

The incidence (frequency) of AEs, TEAEs, ADRs, irAEs, AESIs, SAEs, and AEs resulting in study treatment discontinuation will be summarized. The severity distribution of TEAEs, ADRs, irAEs, AESIs, and AEs resulting in study treatment discontinuation will be summarized using NCI CTCAE v4.03 presented via SOC/PT.

Subjects who discontinue the treatment due to AEs, develop SAE, or die will be listed (include at least the followings: start and end date of the AEs, severity grades, relationship with study drugs, measures taken, and outcomes).

8.4.6.3 Laboratory tests

Measurements and changes after treatment in count of whole blood cells and blood biochemistry parameters will be described using mean \pm SD, maximum, minimum, and median. Normal and abnormal changes after treatment will be described using the cross-classification table.

Routine urinalysis: A cross-classification table is used to describe changes between normalities and abnormalities before and after the treatment.

The proportion of subjects with "clinically significant abnormalities" will be presented. The clinical significance will be determined by the investigator.

Subjects with abnormal changes after treatment (whether clinically significant or not) will be listed.

8.4.6.4 ECG

Descriptive statistics are used for ECG and changes from baseline. A cross-classification table is used to describe ECG and changes from baseline before and after the treatment and data lists will be provided.

8.4.6.5 Vital signs, physical examination and other safety-related examinations

Descriptive statistics of vital signs and relative changes from baseline will be shown.

Abnormal changes from baseline in physical examination will be listed.

8.4.7 Immunogenicity

The rates of ADA and NAB development will be calculated. Subjects' antibody titer will be listed.

8.4.8 Compliance

The frequency and proportion of subjects who violate the treatment regimen will be presented.

The proportion of subjects administered study drug doses between 80–120% of the dose specified in the protocol,

who complete the study, and who complete different number of treatment cycles will also be summarized.

8.4.9 Subjects' baseline characteristics

Subjects' demographics (sex and age), tumor diagnosis information (pathological diagnosis, tumor staging, prior treatment), baseline tumor evaluation (target lesion, number of non-target lesions, sites, total diameter, etc.), and other baseline information (height and weight (BMI, BSA), vital signs, laboratory tests, past/concomitant medications) will be analyzed using descriptive statistics.

8.4.10 Interim analysis

One interim analysis is planned for this study:

Time point for the analysis: after the first 20 subjects have completed the treatment as per the study protocol for the safety evaluation.

8.4.11 Multiple comparisons and adjustments

One interim analysis is planned for this study. The interim analysis will analyze safety data of the first 20 subjects, and the α will not be adjusted.

8.4.12 Subgroup analysis

Treatment efficacy in PD-L1-positive subjects is analyzed.

Subgroup efficacy analyses will be performed based on age and previous treatment.

8.4.13 Eligible subject data lists

In addition to subjects' data list, tumor evaluation (date of evaluation, lesion status, evaluation results) and efficacy endpoints of subjects who have achieved CR and PR will be listed separately.

PFS data of all the subjects at the end of the study will be also be presented.

8.4.14 Exploratory analysis

The association between PD-L1 expression levels and treatment efficacy will be examined using descriptive statistics.

The association between number of TIL and treatment efficacy will be summarized using descriptive statistics.

The association between dynamic changes in EBV DNA copy number and treatment efficacy will be presented using descriptive statistics.

Dynamic changes in immune cell phenotypes in peripheral blood will be summarized using descriptive statistics, and the potential association with efficacy will be explored.

The correlation between immune-related cytokines IL-6, IL-15, TNF- α and soluble PD-L1 and efficacy of anti-PD-1 treatment will be presented using descriptive statistics.

8.5 Sample size estimation

This is a single-arm trial. The primary objective is to evaluate the efficacy of IBI308 monotherapy for the treatment of relapsed or refractory extranodal NK/T-Cell Lymphoma. 20-60 subjects will be enrolled. Assuming a null hypothesis of 30% ORR, α of 0.05 (two-sided), power of 80%, a 50% ORR after IBI308 treatment will be achieved and the minimum sample size will thus be 43.

The sponsor will evaluate the safety data from the first 20 subjects to determine whether the study shall be discontinued prematurely due to safety concerns.

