## 1.3 SAMPLE SIZE

The hypothesis of this study is to evaluate the effectiveness of ORR based on Lugano 2014:

H0: ORR $\leq$ 30%

H1: ORR $>$ 30%

For the primary efficacy endpoint ORR, the point estimate and its (100- $\alpha$ )% confidence interval ( $\alpha$  maybe different from 5 if interim analysis is added) will be provided using binomial distribution. If the lower limit of the confidence interval is greater than 30%, the effectiveness of IBI308 is established for r/r ENKTL. This is a single-arm trial, and 20-60 subjects are planned to be enrolled for the study. Under the assumption of an ORR=50%, with 43 subjects, there is 80% power to reject H0 under a two-sided type I error rate of 0.05.

After first 20 subjects enrolled, a safety evaluation will be conducted before continuing enrollment.

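### Planned enrolment of 20-60 starts below the protocol's own minimum of 43, so neither that size nor the 80% power tied to it is secured by the design

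*Protocol*

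**What the plan says.** Protocol 8.5 says "20-60 subjects will be enrolled". Its next sentence, on a null ORR of 30%, a target of 50%, two-sided alpha of 0.05 and 80% power, concludes that "the minimum sample size will thus be 43". The Statistics part of the synopsis has the same text.

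SAP 1.3 repeats the range ("20-60 subjects are planned to be enrolled for the study") but words the power differently: "with 43 subjects, there is 80% power to reject H0 under a two-sided type I error rate of 0.05". It does not call 43 a minimum.

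Success requires the lower confidence limit for ORR to lie above 30% (protocol 8.2, SAP 1.3). SAP 5.5.1 specifies a 95% interval from the exact binomial distribution. The only stated reason to stop near 20 subjects is safety (protocol 8.5), and protocol 8.4.11 makes no alpha adjustment for that look.

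The Summary of Amendment, used here only as context, says that 28 patients had been enrolled when the range replaced a minimum of 60.

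**The concern.** A planned range that starts at 20 and a minimum of 43 cannot both describe the same trial. Of the 41 sizes from 20 to 60, 23 (20 to 42) lie below the minimum. No passage sets the point at which enrolment ends, and none makes the primary test depend on reaching 43. A trial that closes at 25 or 30 subjects has followed the plan as written, yet the protocol still tells its reader that 43 is the least that gives 80% power.

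What is at stake is the accuracy of the stated power. If the drug works as assumed and the trial closes at a small size, the chance of missing the effect is well above the 20% that the protocol implies.

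**Working it through.** **Inputs.** Null ORR p0 = 0.30, target ORR p1 = 0.50, two-sided alpha 0.05, power 0.80, stated size 43 and range 20-60 (protocol 8.5, SAP 1.3). Success means a lower limit above 30% (protocol 8.2, SAP 1.3), from an exact binomial 95% interval (SAP 5.5.1). "Exact" is taken as Clopper-Pearson.

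**Step 1: reproduce 43.** The normal approximation with null and alternative variances is

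n = [(z0.975·√(p0·q0) + z0.80·√(p1·q1)) / (p1 − p0)]²

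= [(1.960 × 0.4583 + 0.8416 × 0.5) / 0.20]² = (1.3190 / 0.20)² = 43.49.

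This is 43 when rounded (44 when rounded up). Power at 43 by the same approximation is Φ[(0.20·√43 − 1.960 × 0.4583) / 0.5] = Φ(0.827) = 79.6%. The 43 therefore reproduces.

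**Step 2: power across the range.** For each n, find the smallest number of responders x whose exact lower limit exceeds 0.30. Power is P(X ≥ x) with X ~ Bin(n, 0.50). The fixed-size error is the same tail probability at 0.30.

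| n | Responders needed | Exact power at 50% | Fixed-n error at 30% | Power by the step 1 approximation |
|---|---|---|---|---|
| 20 | 11 (55.0%) | 41.2% | 0.017 | 49.7% |
| 28 | 14 (50.0%) | 57.5% | 0.021 | 62.6% |
| 43 | 20 (46.5%) | 72.9% | 0.016 | 79.6% |
| 60 | 26 (43.3%) | 87.75% | 0.020 | 90.4% |

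Below 43, the highest exact power is 73.9%, at n = 39. Over the whole range, 31 of the 41 sizes have exact power below 80%. The largest fixed-n error anywhere in the range is 0.024, below the one-sided 0.025.

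**Step 3: an observed ORR equal to the 50% target.** Exact lower limits:

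- 10/20: 27.2%, fails
- 11/22: 28.2%, fails
- 12/24: 29.1%, fails
- 13/26: 29.9%, fails
- 14/28: 30.6%, passes

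At 27 subjects the rule needs 14 responders (51.9%).

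**Step 4: does the interval matter?** The 10/20 result also fails by Wilson (29.9%) and Wald (28.1%). With Wilson limits, power is 57.5% at 28 and 82.0% at 43, and the highest value from 28 to 42 is 79.1% (at 38). The figure at 43 depends on the method. The shortfall at 28 does not.

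**The case against.** The strongest reply is that sizes of 20 to 27 were no longer possible when this text was adopted, because 28 patients were already enrolled. A reader might infer from the range that the trial could close at 20 and fail on its own 50% target. The documents do not support that as a practical outcome: at 28 enrolled, 14/28 just passes. What remains is narrower. The FAS excludes subjects without a measurable lesion at baseline and provides for exclusion on central pathology review (protocol 8.3, SAP 3.1). One or two exclusions from 28 would bring the analysed set to 27 or 26, where an observed 50% no longer suffices.

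Three further replies carry weight:

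- The SAP's power statement is conditional on 43 subjects and is not in itself a claim about smaller sizes. The misleading wording is mainly the protocol's "minimum".
- Low power raises the risk of a missed effect, not of a false claim. The amendment summary reports a 67.9% ORR in 28 patients (19/28), with an exact lower limit of 47.6%. Restating power would not change that reading.
- The range was a deliberate and explained change, and its lower end matches the 20-subject safety look. Neither document gives that look as the reason for the lower bound, so this softens the inconsistency without removing it.

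**Conclusion.** The point holds as an internal inconsistency in protocol 8.5 and the synopsis, carried into SAP 1.3 by the repeated range. The design does not secure 43 subjects or 80% power. Under the SAP's exact rule at a true ORR of 50%, power is about 41% at 20, 57% at 28, 73% at 43 and 88% at 60. At 28, the smallest final enrolment still possible, the shortfall from 80% is about 22 percentage points by the exact rule and 17 by the plan's own approximation.

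Two stronger readings should not be drawn. The 43 is not miscalculated, since it follows from a standard normal approximation. Nor does the range by itself create a false-positive risk, since the error at each fixed size stays below 0.025. That last statement covers a fixed size only. Whether choosing the size after seeing responses affects error is a separate question, not assessed here.

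The conclusion assumes Clopper-Pearson limits, no alpha adjustment, and an analysed set equal to the number enrolled. FAS exclusions would change the size used in the test.

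**What to change.** In protocol 8.5, the synopsis and SAP 1.3:

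- Keep 20-60 as the enrolment range, but stop presenting 43 as a minimum and 80% as the trial's power. Describe 43 as the size given by the normal approximation.
- State the power under the SAP's exact rule at a true ORR of 50%: about 41% at 20, 57% at 28, 73% at 43 and 88% at 60.
- Say that a final size below 43 falls short of the sample-size assumption.

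Replacing the range with a single planned number of 43 at 80% power would not resolve the matter, because the exact rule gives 72.9% there.

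The cost is wording in three places and a less favourable stated power. No extra patients are needed, and neither the test nor the analysis changes.

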8.6 Methods for Controlling Bias

8.6.1 Randomization and blinding

This is a single-arm, open-label study. There is no randomization or blinding.

8.6.2 Blinding maintenance evaluation

Not applicable.

8.6.3 Emergency unblinding

Not applicable.

9 Quality assurance and quality control

In accordance with GCP guidelines, the sponsor is responsible for the implementation and maintenance of quality assurance and quality control systems as per appropriate standard operating procedures to ensure the study is implemented and authentic data is collected, documented, and reported in accordance with the requirements of the protocol, GCP, and applicable regulations.

9.1 Clinical monitoring

The sponsor or its authorized contract research organization (CRO) will conduct clinical monitoring of this study. The clinical research associate (CRA) shall perform the monitoring in accordance with the standard operating procedures provided by the sponsor or CRO, and has the same rights and responsibilities as the sponsor's CRA. The CRA must maintain regular communication with the investigator, authorized research personnel, and sponsor.

Before the study begins, the CRA will assess the competency of each study site, and report issues related to facilities, technical equipment, and medical personnel to the sponsor. During the course of the study, the CRA is responsible for the monitoring of whether the written ICF from all subjects has been obtained and whether the data records are correct and complete. The CRA shall compare the data inputted in the eCRFs with the raw data, and inform the investigator of any errors or omissions. Besides, the CRA will also control the compliance of the protocol and study procedures for each study sites, arrange for the supply of investigational drug, and ensure that the drug is kept under proper conditions.

The monitoring visits shall be conducted in accordance with the requirements of relevant laws and regulations. From the time the subjects are enrolled, each center shall receive regular visits for the purpose of monitoring. After each visit to the investigator, the CRA shall submit a written report to the sponsor.

9.2 Data Management/Coding

This study will use an electronic data collection (EDC) system, and the research data will be recorded in the eCRFs by the investigators or its authorized personnel. Before the initial of the study site or data entry, the investigators and authorized personnel shall be properly trained and appropriate security measures shall be taken for the computer and other equipment.

Data entry into the eCRFs shall be completed as soon as possible during or after visiting. The eCRFs shall be updated at any time to ensure that they reflect the latest data of the subjects. To avoid the differences in outcome evaluations by different evaluators, it is recommended that the baseline and all the subsequent efficacy and safety evaluations of a given subject shall be performed by the same individual. The investigators are required to review the data to ensure the accuracy and correctness of all the data entered into the eCRFs. If no evaluations are conducted during the study, or some obtained information are not evaluable, not applicable, or unknown,

the investigators shall record the above information in the eCRFs. The investigator shall sign the verified data electronically.

The CRA will review the eCRFs, and evaluate the completeness and consistency by comparing with the source document to ensure consistency of key data. Data entry, corrections, and modifications shall be performed by the investigator or designee. The data in the eCRFs is submitted to the data server and any modifications in the data shall be recorded in the audit trail, including reasons, operator names, time, and dates of modification. The roles and permission levels of the personnel responsible for data entry in the study site will be determined in advance. The CRA or data management personnel may raise an inquiry in the EDC in the event of suspicious data. The study site personnel are responsible for dealing with such inquiry. The EDC system will record the audit trail of the inquiry, including the investigator name, time, and date.

Unless otherwise stated, the eCRFs shall only be used as forms to collect data, instead of source. The source documents are used by the investigators or hospital, including all records related to the subjects, which are able to demonstrate the presence, inclusion criteria, and participation of subjects (laboratory records, ECGs, pharmaceutical records, subject folders, etc.).

The investigator is responsible for the maintenance of all source documents and shall offer the documents to the CRA for review during each visit. In addition, the investigator must submit a complete eCRF for each enrolled subject, regardless of the duration of participation. The protocol number and subject numbers of all supporting documents (such as laboratory records or hospital records) submitted with the eCRFs shall be carefully verified. All the personal privacy information (including the subjects' names) shall be deleted or made illegible to protect the privacy of the subjects. The investigator verifies that the record has been reviewed using an electronic signature and ensures the accuracy of the recorded data. The electronic signature shall be completed using the investigator's user ID and password. The system will automatically attach the date and time of signing to the signature. The investigator must not share his/her user ID and password with others. If the data in the eCRFs are required to be changed, the change shall be performed according to the procedure outlined by the EDC system. All the changes and corresponding reasons shall be recorded in the audit trail.

AEs and concomitant diseases/history shall be coded. The dictionary for coding will be described in the Clinical Study Report (CSR).

